##### <Principle>

Put the catheter in the catheter case filled with disinfectant.  
In case of carrying, it is possible to bend the catheter with catheter case concurrently.

##### [Intended Usage, Indications and Effect]

The device is to be inserted temporarily into the patient's urethra, bladder, ureter, or drainage port after urinary diversion surgery to be used for urination.

##### [Specification of Component]

The catheter can endure the pull strength from the both ends at the load of 4.9 N without tear.

##### [Operation Procedure]

A typical operation procedure is described below:

- 1) Straighten the catheter case and fill the catheter case with a disinfectant of right concentration. See the following drawing as target amount of solution (Figure 1).

[figure not shown]

Figure 1

2) Push the cap into the funnel until the chase of the cap places at the second lib of the funnel in order to fix firmly. (Figure 2).

Figure 2

3) Straighten the catheter case and insert the catheter with cap into the catheter case. Turn the cap surely and lock it in firmly. And make sure that disinfectant is not leaked from the catheter case.  
 4) Pull out the catheter and take urination procedure.  
 5) After use, clean the catheter with tap water, boiling and so on. And then house and store it into the catheter case filled by disinfectant according to the steps 2) to 3) of [Operation Procedure].  
 6) After bending the catheter case and keep the bended form by hook, put it in the outer case.

**<Precautions related to the operation procedure>**

When place the funnel into the cap, push the funnel to specific position (See figure 2).

After screw the cap, make sure the catheter case and the cap fix completely, and disinfectant does not leak from the case.

[Leakage of disinfectant may occur]

**[Precautions]**

**<Important general instructions>**

1) In case of not use this device for long time, do not bend the catheter case. Straighten the catheter case when it stores.  
 2) Prescribe an appropriate disinfectant of right concentration for the patient. Below provides the drug name and the reference concentration for use, for information. However, the concentration must be decided considering the patient conditions based on the physician's experiences.

Generic name	Reference concentration for use	Usage experience
sodium hypochlorite	0.0125~0.02%	Dilute "Milton" 50 to 80 times with water

Generic name	Reference concentration for use
Benzalkonium chloride solution	0.05~0.1%
Benzethonium chloride solution	0.05~0.1%

Note) The device may be colored depending on the disinfectant used.  
 3) Before using this product, check every component for any abnormalities.

- Do not insert the catheter forcibly. If there is difficulty in insertion, stop the use and take appropriate measure.  
 [Otherwise, it may harm the patient's tissues.]
- Avoid forcible insertion or removal, and operate with a good care.  
 [Otherwise, it may cause breakage of the device.]
- If there is any abnormality, stop the use immediately and take appropriate measures.
- If upon use of the device, do not pull or bend it forcibly. Handle it gently and carefully.
- Do not modify the product.  
 [If any feature (e.g. side hole(s)) is added, it may cause breakage of the catheter.]
- Do not expose this product to an organic solvent, strong acid, strong base, or any equivalent agent.
- Do not hold this product strongly with forceps or other tool.  
 [Otherwise, it may cause a tear of the catheter or clogging in the lumen.]
- In case of any abnormality including damage in the package or the device, do not use the product.  
 When is found on the label, it means that the product should not be used if the package has been damaged or opened.
- After opening, use the device appropriately. After replaced to a new device, the obsolete device should be disposed in a safe manner.
- When is found on the label, it means the product doesn't contain DEHP in the contact part with body fluid and drug solution.

**<Adverse events>**

- Urethralgia or distress during catheter insertion at initial period of self-catheterization.
- Urinary tract infection such as cystitis or pyelonephritis.  
 [In the case of having a small urinary volume every day or a difficulty in keeping herself/himself clean.]
- False passage (In case of male)  
 [Forcible catheter insertion]
- Leakage of disinfectant.

**[Method of Storage and Shelf Life]**

**<Method of storage>**

This product must be stored under clean conditions and prevented from direct sunlight, high temperature and humidity, low temperature below 10°C, and ultraviolet ray including a sterilizer.

**<Useable period>**

[figure not shown]
This product is recommended to be replaced with a new device within 1 month.

**<Shelf life>**

- Follow the proper storage methods, and use the use before date printed on the each package.
- Store the product with great care, and do not use the device if it passed the use before date.

**[Packaging]**

5 sets/box.

DC61484RN-2 (DC 67022.9) 2018.7.18

## Appendix B: ISC-Q index score

	Strongly disagree	Slightly disagree	Neither agree nor disagree	Slightly agree	Strongly agree
Ease of use					
1. It is easy to prepare my catheter for use each time I need it					
2. It is messy to prepare my catheter for use					
3. It is easy to insert my catheter					
4. I find inserting the catheter is uncomfortable sometimes					
5. The design of the catheter makes it easy to insert					
6. The catheter is fiddly to use					
7. The lubrication on the catheter makes it difficult to use					
8. I feel confident in my ability to use my catheter					
Convenience					
9. Storage of catheters at home is inconvenient					
10. Taking enough catheters for a weekend away is very inconvenient					
11. Taking enough catheters for a 2-week holiday is very inconvenient					
12. Disposal of my catheter is inconvenient when away from home					
Discreetness					
13. I find it easy to carry enough catheters around with me on a day-to-day basis					
14. I find it easy to dispose of my catheter when I am away from home					
15. My catheter is discreet					
16. I can use my catheter discreetly when I am away from home					
17. I can easily dispose of my catheter without it being obvious to people					
18. My catheter allows me to feel confident when away from home					
Psychological well-being					
19. I am self-conscious about my need to self-catherize					
20. I would feel embarrassed if people saw my catheter in its packet					
21. My need to use a catheter sometimes makes me feel embarrassed					
22. I worry that my catheter doesn't always empty my bladder fully					
23. My need to use catheters stops me from visiting friends and family as often as I would like					
24. I worry about the risk of long-term problems from using my catheter					

## Appendix C: InCaSa questionnaire score

Items and dimensions of the Intermittent Catheterization Satisfaction Questionnaire (InCaSaQ, English translation of the original validated questionnaire written in French).

Question		Not satisfied at all = 0	Slightly satisfied = 1	Satisfied = 2	Extremely satisfied = 3
Packaging	Concerning discretion and bulk of the package, are you?	0	1	2	3
	Concerning hygiene and robustness of the package, are you?	0	1	2	3
Lubrication	Concerning the opening and possible fixation of the catheter, are you?	0	1	2	3
	Concerning the means used for lubrication (spontaneous, gel, water, ...), are you?	0	1	2	3
Catheter itself	Concerning holding, pushing and insertion into the urinary meatus, are you?	0	1	2	3
	Concerning ease of progression and insertion comfort, are you?	0	1	2	3
After catheterization	Concerning the ease with which you could void (length of the catheter and catheter accessories), are you?	0	1	2	3
	Concerning the ease with which your catheter could be disposed of, are you?	0	1	2	3

## Appendix D: Perception questions

Perception Questionnaire:

Handling	Very difficult	Difficult	Neither Difficult nor Easy	Easy	Very easy	Don't know
How was it to prepare the catheter						
How was it to insert the catheter?						
How was it to empty the bladder?						
How was it to withdraw/remove the catheter?						
How was it to clean the catheter						
How was it to store the catheter						
How was it to perform a hygienic catheterization?						
How was the overall experience (from preparation to storage/disposal) of the catheter						
Confidence and in control	Strongly disagree	Slightly Disagree	Neither agree nor disagree	Slightly Agree	Strongly agree	Don't know
It was possible to perform a hygienic catheterization						
It was possible to perform the overall procedure (from preparation to storage/disposal) within reasonable timeframe						
I feel in control when inserting the catheter						
I feel confident when inserting the catheter						
I feel in control when withdrawing the catheter						
I feel confident when withdrawing the catheter						
Sensation	Strongly disagree	Slightly Disagree	Neither agree nor disagree	Slightly Agree	Strongly agree	Not applicable (lack of sensation)
It feels gentle to insert the catheter						
It feels gentle to withdraw the catheter						
I have felt resistance during withdrawal						
I have felt a blocking sensation during catheterization						
I have felt pinching/sting during catheterization						
Satisfaction	Strongly disagree	Slightly Disagree	Neither agree nor disagree	Slightly Agree	Strongly agree	Don't know
I am satisfied with the catheter						
I would recommend the catheter to others						
I would like to continue using this catheter						
I am concerned about risk of infection						
Convenience	Strongly disagree	Slightly Disagree	Neither agree nor disagree	Slightly Agree	Strongly agree	Don't know
I found the overall procedure (from preparation to storage/disposal) convenient						

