## 2. Rational/justification for conducting the clinical investigation

In patients with neurogenic or non-neurogenic bladder dysfunction, intermittent catheterization (IC) is a well-accepted tool for bladder management, ensuring patient independence and improved quality of life.

To minimize the risk of urinary tract infections (UTIs), the use of sterile, single use catheters has for many years been the recommended standard of care. However, based on cost and an environmental agenda, a push for reuse catheters has emerged. International associations do not currently endorse catheter reuse due to the lack of standardized cleaning and reuse recommendations and a concern of decreased compliance, unsafe practice and increased risk of UTIs. There is at present a lack of solid evidence with respect to risk of UTIs associated with single use vs. reuse, though one recent metanalysis including > 900 users found single use catheters to be the only catheter associated with reduced UTI rate.

Deciphering the influence of catheter per se is complicated by the highly complex and multifactorial causalities associated with UTIs in IC users, however, a recent study demonstrated significant bacterial contamination on reuse catheters. Also, there was an end-study preference towards single use and increased health-related (HR) QoL, when changed from reuse to single use catheter. These results align well with user concerns, namely, the risk of UTIs and the burden of repeated daily cleaning procedures.

In alignment with these concerns, the aim of the present investigation is to investigate potential user challenges and level of catheter contamination, associated with introducing re-use catheters in a patient population accustomed to single use catheters. Thus, addressing the influence of catheter choice on HR-QoL and treatment satisfaction, the primary aim of this investigation is to analyse single use vs. re-use, using validated IC-specific questionnaires. To better evaluate the risk of potential catheter contamination at time of catheter reuse, the secondary aim is to analyse bacterial colonization after catheter cleaning and storage, just prior to catheterization.

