### 5.6. Equipment/methods and timing for assessing the variables

The primary endpoint is evaluation of HR-QoL assessed at Baseline Visit (V1) based on use of the single use intermittent catheterization and assessed after 28 days at Termination Visit (V5) based on use of the reuse catheter. HR-QoL will be measured by the ISC-Q index score.

The secondary endpoint will be an evaluation of adverse events from time of signed informed consent and throughout the test period.

The exploratory endpoints will be collected with satisfaction questionnaire score and perception questions at visit 1 and visit 5.

Evaluation of intermittent catheterization satisfaction assessed at Baseline Visit (V1) and after 28-days of using the re-use catheter CLINY, at the Termination Visit (V5). For this assessment the InCaSA – Intermittent Catheterization Satisfaction Questionnaire will be used.

Evaluation of intermittent catheterization related to perception will be assessed at Baseline Visit (V1) and after 28-days of using the reuse catheter CLINY, at the Termination Visit (V5). For this assessment, perception questions on a 6-point scale will be used for measuring of this endpoint.

Evaluation of total catheter-associated bacterial count and number of bacterial-positive catheter samples:

In a laboratory at Coloplast the total catheter-associated bacteria count (CFU/mL) will be assessed for all CLINY catheters collected at Termination Visit (V5). The number of bacterial-positive catheter samples will also be assessed, where positive is defined as presence of any detectable concentration. The data will be compared to a baseline evaluation of the CLINY catheter-associated bacterial count and number of bacterial-positive catheter

samples. In total 6 single use hydrophilic coated catheters taken directly from packages will be assessed, thus no bacteria are expected on the samples.

See Flowchart table 5 for further information regarding timing of endpoint data capture.

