##### **Baseline Visit (V1), Week 0: Day 0**

- Introduction to the investigation reviewed and confirmed
- Informed Consent signed
- Check of in- and exclusion criteria
- Urine dipstick for hematuria, leucocytes, and nitrite level (Appendix F and G)
- For female subjects of childbearing potential: urine pregnancy dipstick
- Enrolment in the investigation and allocation of subject number
- Collect Baseline information:
  - Gender (male/female)
  - Age (at time of enrolment in years)
  - Height (in cm)
  - Weight (in kg)
  - Reason for using intermittent catheterization
  - When did you start using a catheter? (months/years)
  - Current single use catheter: brand/material/product/item number (at time of enrolment)
  - Single use catheter size at time of enrolment
  - Average number of catheters used per day during the last 1 month
  - Time spent on each catheterization from preparation to storage/disposal (in minutes)

- What is your handedness?
  - Right-handed
  - Left-handed
  - Mixed or cross-dominant (i.e., changes according to task)
  - Ambidextrous (i.e., equal ability in both hands)
- What is your urethral sensation?
  - Normal
  - Impaired
  - Hypersensitive
  - None
- What is your hand dexterity (left/right)?
  - Left hand:
    - Normal dexterity
    - Reduced dexterity
    - Greatly reduced dexterity
    - Don't know
  - Right hand:
    - Normal dexterity
    - Reduced dexterity
    - Greatly reduced dexterity
    - Don't know

- Review of concomitant medication at time of enrolment
- Instruct the subject in completing the Baseline questionnaires for evaluation of single use catheter:
  - ISC-Q assessment (paper) (Appendix B)
  - InCaSa assessment (paper) (Appendix C)
  - Perception assessment (paper) (Appendix D)
- Distribution of CLINY Self-Catheterization Set and investigational supplies
- Instruct the subject in use of CLINY according to the IFU (Appendix A)
- Instruct the subject in use of weekly urine dipstick form
- Insurance of subjects' compliance with the CIP
- Scheduling Phone Call Visit (V2) in Week 1, 7 days +/- 1 day after Baseline Visit (V1)
- Complete eCRF

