#### **Termination Visit (V5), Week 4: Day 28 (+/3 days)**

- Review of Adverse events/Serious adverse events/Adverse device events, device deficiencies and Protocol Deviations
- Review of changes in concomitant medication
- Evaluation of catheterization since last visit:
  - Have the subject used single use catheters since last Phone Call Visit
  - Did the subject follow all cleaning procedures stated in the IFU?
  - Average number of daily catheterizations with CLINY the subject completed since Phone Call Visit

- Average time spent on each catheterization from preparation to storage/disposal (in minutes)
- Instruct the subject in completing the Termination questionnaires for evaluation on the test period with reuse catheter, CLINY Self-Catheterization set:
  - ISC-Q assessment (paper) (Appendix B)
  - InCaSa assessment (paper) (Appendix C)
  - Perception assessment (paper) (Appendix D)
- Preference: (See Appendix E)
  - Catheter preferred (paper)
  - Reason for preference (paper)
  - Consideration to switch to a reusable catheter in the future (paper)
- Reason for drop out if Termination Visit is performed prior to 28 test days
- Urine dipstick for hematuria, leucocytes, and nitrite level (Appendix F & G)
- Review of weekly urine dipstick form for completeness and compliance.
- Ensure of the subjects' wellbeing and compliance with the CIP
- Collect CLINY Self-Catheterization Set. The catheter should be stored in the catheter case WITHOUT Milton solution
- Send CLINY Self-Catheterization set for Laboratory assessments and analysis
- Perform device accountability
- Complete eCRF

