## 10. Statistical considerations

### 10.1. Statistical design, method, and analytical procedures

Baseline assessments and endpoints will be reported by descriptive statistics and/or listed. Summaries will be presented by device i.e., IC and re-use catheters and if relevant, by other grouping variables.

Descriptive statistics for continuous variables are presented with N, Mean, SD (standard deviation), Median, Min and Max, where N denotes the number of subjects contributing with non-missing data. For discrete variables, descriptive statistics are presented with N and percentage, where percentage is based on the total number of subjects/observations with non-missing data.

All statistical analysis will be performed with [REDACTED]

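### The perception item on cleaning is also asked about the single use catheter at V1, where it cannot apply, so it should be reported for CLINY at V5 only (minor)

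*Combined protocol and SAP*

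**What the plan says.** Appendix D is the perception questionnaire. Its Handling block includes the item "How was it to clean the catheter". The answers run over five ordered options from very difficult to very easy, with "Neither Difficult nor Easy" in the middle, and a sixth option, Don't know. An inapplicability option appears in one block only, Sensation, where it reads "Not applicable (lack of sensation".

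The same form is used at both visits, for different catheters. Section 7.1, Baseline Visit (V1), tells the site: "Instruct the subject in completing the Baseline questionnaires for evaluation of single use catheter", and lists the perception assessment (Appendix D). Section 7.1, Termination Visit (V5), says: "Instruct the subject in completing the Termination questionnaires for evaluation on the test period with reuse catheter, CLINY Self-Catheterization set", and lists the same appendix. Section 5.6 confirms the timing: "Evaluation of intermittent catheterization related to perception will be assessed at Baseline Visit (V1) and after 28-days of using the reuse catheter CLINY". The flow chart (Table 5) and Appendix H agree. Nothing removes the cleaning item from the V1 form.

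For reporting, section 10.1 states: "Summaries will be presented by device i.e., IC and re-use catheters". Discrete variables get N and percentage over non-missing answers. Section 10.4 limits the exploratory endpoints, which include perception, to descriptive statistics.

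**The concern.** The form assumes that every item makes sense for both catheters. The cleaning item does not. Subjects enter as users of a single use hydrophilic catheter, which is discarded after use, so at V1 they have no cleaning step to rate. They may choose very easy because there is no work, choose the midpoint, choose Don't know, or try to leave the line blank. The choice reflects how they read the question.

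The topic is not a side issue. Section 2 names two user concerns about reuse: "the risk of UTIs and the burden of repeated daily cleaning procedures". Section 3.1 makes perception compared with single use one of the secondary objectives. If the item is tabulated by device as planned, a reader may take the single use column as a baseline rating of cleaning and read the difference from CLINY as a measured change.

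**Working it through.** **The plan's own figure.** The endpoint is described as a 6-point scale. The Handling block has 5 ordered ratings + 1 Don't know = 6, so the figure is reproduced. Only five of the six points are ratings.

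**Item count (Appendix D).** Handling 8, confidence and control 6, Sensation 5, Satisfaction 4, Convenience 1: 8 + 6 + 5 + 4 + 1 = 24. Not applicable is offered for the 5 Sensation items, so 24 − 5 = 19 items lack it, the cleaning item among them. The affected share is 1 of 24 items, or 1 of 8 in the Handling block.

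**Is cleaning rated anywhere else?**
- ISC-Q (Appendix B): 24 items on preparation, insertion, storage, disposal, discretion and worry. None names cleaning.
- InCaSa (Appendix C): 8 items. One concerns hygiene of the packaging; none names cleaning the catheter.
- Phone visits V2 to V4 and V5 (section 7.1): subjects are asked whether they followed the cleaning procedures in the instructions for use. This is a direct question about cleaning, but it checks adherence with CLINY. It is not a rating and is not asked about the single use catheter.

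So the Appendix D item is the only one that names cleaning among the rating questionnaires completed by the subject.

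**What the single use column would hold.** Assume, for illustration, that all 40 planned subjects answer at V1 and a share d ticks Don't know. The number of difficulty ratings is 40 × (1 − d):

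| d | Difficulty ratings at V1 |
|---|---|
| 0% | 40 |
| 25% | 30 |
| 50% | 20 |
| 75% | 10 |
| 100% | 0 |

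In no row does a rating refer to a cleaning step. The percentages also depend on an unstated convention. Take d = 50% and let the other 20 all tick very easy. If Don't know counts as non-missing, very easy is 20/40 = 50%. If it is set to missing, very easy is 20/20 = 100%. Section 10.1 does not say which applies.

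**Blank answers.** Section 9.1.3 has the monitor use edit checks so that all eCRF fields are completed. That pushes towards a ticked answer.

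**The case against.** Five points can be made in the plan's favour.

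1. *Subjects are not forced to invent a rating.* Don't know is a way out, and in an N and percentage table a cluster of such answers at V1 would be visible. This stands in part. Don't know still merges having no cleaning to do with having no opinion, and no rule says how it is tabulated.

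2. *Very easy may be an honest answer.* A user may mean that no cleaning is needed, which is a true difference between the devices. That is possible. But it is known from the design, and it cannot be told apart from the other readings of the question.

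3. *Cleaning burden can be compared without this item.* This stands. Time per catheterization, from preparation through storage or disposal, is collected for the single use catheter at V1 and for CLINY at V2 to V5. Three Appendix D items cover the whole procedure and apply to both devices: overall experience, reasonable timeframe and convenience. A reader might infer that the trial loses its comparison of burden, or that this is its only direct question on cleaning. The documents support neither, given these items and the adherence question at V2 to V5.

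4. *The plan can set the answers aside.* Section 10.2 allows individual data points to be excluded with documentation, and section 10.1 allows listing. Both are discretionary. Neither stops the item being collected at V1 or keeps it out of the by-device table.

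5. *Nothing formal depends on it.* This stands. Perception is exploratory and descriptive, with no test or pass/fail criterion.

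**Conclusion.** The point holds, as a minor one. Following the plan as written yields a single use column for an item that has no meaning for a single use catheter, placed beside a meaningful CLINY column. It affects 1 of 24 items of a descriptive exploratory endpoint. The ISC-Q analysis, the significance level, the sample size and the CLINY answers at V5 are untouched.

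A reader might want to score the answers 1 to 5 and quote a spurious mean change in points. The documents do not support such a figure: they specify no numerical scoring, item mean, change score or Handling subscale for Appendix D, and they do not say how subjects would answer at V1.

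The conclusion rests on one inference, that a single use catheter is not cleaned by its user. The documents do not say so in words, but it follows from the term. It also assumes that the V1 form is Appendix D as printed, which is what section 7.1 cites.

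**What to change.** Either omit the cleaning item from the V1 form, or add an answer at V1 such as *Not applicable, I do not clean my catheter*. In the reporting plan, state that the item is summarised at V5 for CLINY only, as N and percentage per category with Don't know shown as its own category, and with no single use column and no V1 to V5 comparison. If V1 forms are already in use, the reporting rule alone is enough.

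The cost is one line on a paper form and one row of a table shell. No cleaning experience goes unrecorded, because none exists at V1. The comparison of burden between devices can rest on time per catheterization and the overall-procedure items, which are already collected for both.
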